## **4.3 Description of Study Procedures**

### **4.3.1 Efficacy**

#### **4.3.1.1 Crohn's Disease Activity Index**

The CDAI is a composite index with weighted domains that quantifies the global disease severity in a single numerical score. It is the oldest and most widely used of several multi-item instruments that have been developed and is validated for use in clinical studies to measure disease activity in CD (Best et al, 1976; Sands and Ooi, 2005). The CDAI measures the severity of active disease using symptom scores that are monitored over the previous week and includes subject-reported symptoms, physician-assessed signs, and laboratory markers. The CDAI score is calculated by summing weighted scores for subjective items (number of liquid or very soft stools, abdominal pain and general well-being) recorded by a diary during a 1-week period, and objective items (associated symptoms, taking antidiarrheal agents such as loperamide/opiates, abdominal mass, hematocrit, daily morning temperature,

and body weight). The CDAI scores range from 0 to 600, with higher scores indicating greater disease activity. Subjects with scores of < 150, 150 to 219, and 220 to 450 represent remission, mild disease, and moderate to severe disease, respectively; whereas subjects with scores of > 450 have very severe disease (Buxton et al, 2007). The CDAI will be calculated at the site in order to determine the eligibility for the study.

The CDAI assessments will be performed at each study visit starting with Visit 2.

[REDACTED]

[REDACTED]

[REDACTED]

[REDACTED]

[REDACTED]

[REDACTED]

[REDACTED]

[REDACTED]

[REDACTED]

[REDACTED]

[REDACTED]

[REDACTED]

[REDACTED]

[REDACTED]	[REDACTED]	[REDACTED]	[REDACTED]	[REDACTED]
[REDACTED]	[REDACTED]	[REDACTED]	[REDACTED]	[REDACTED]
[REDACTED]	[REDACTED]	[REDACTED]	[REDACTED]	[REDACTED]
[REDACTED]	[REDACTED]	[REDACTED]	[REDACTED]	[REDACTED]
[REDACTED]	[REDACTED]	[REDACTED]	[REDACTED]	[REDACTED]

[REDACTED]

[REDACTED]

[REDACTED]

[REDACTED]	[REDACTED]	[REDACTED]	[REDACTED]	[REDACTED]	[REDACTED]	[REDACTED]
[REDACTED]	[REDACTED]	[REDACTED]	[REDACTED]	[REDACTED]	[REDACTED]	[REDACTED]
[REDACTED]	[REDACTED]	[REDACTED]	[REDACTED]	[REDACTED]	[REDACTED]	[REDACTED]
[REDACTED]	[REDACTED]	[REDACTED]	[REDACTED]	[REDACTED]	[REDACTED]	[REDACTED]
[REDACTED]	[REDACTED]	[REDACTED]	[REDACTED]	[REDACTED]	[REDACTED]	[REDACTED]
[REDACTED]	[REDACTED]	[REDACTED]	[REDACTED]	[REDACTED]	[REDACTED]	[REDACTED]

[REDACTED]

[REDACTED]

[REDACTED]

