##### **4.8.4.1 Primary Efficacy Analysis**

The primary analysis will be conducted in the ITT population. The primary efficacy endpoint is CDAI remission at Week 8 of the induction period. The primary comparison of interest will be MEDI2070 high dose group versus placebo. The comparisons between MEDI2070 high-medium dose group versus placebo, low-medium dose group versus placebo, and MEDI2070 low dose group versus placebo will also be conducted.

Missing data will be handled using the non-responder imputation method through the end of the placebo-controlled, double-blind period; ie, any subject with missing information on the primary endpoint will be assumed as a non-responder. In addition, subjects with a clinically meaningful increase in steroid use will also be assumed to be non-responders for the primary analysis perspective. Clinical meaningful increase in steroid dose is defined as an increase of at least 5 mg/day for at least 3 days of prednisone, or equivalent, or an increase of at least 3 mg/day for at least 3 days of budesonide.

The difference in CDAI clinical remission rates at Week 8 between MEDI2070 dose groups and placebo group and associated 90% confidence interval will be provided. P-values for comparisons between any MEDI2070 dose group and placebo will be obtained from a logistic regression model adjusting for the number of prior anti-TNF $\alpha$  agents that failed or were not tolerated (1 vs > 1). In the event the number of remissions is too small (ie, < 5), the exact logistic regression will be performed instead. The statistically significant treatment effect will be tested against two-sided alpha level of 0.10.

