##### **3.6.1.2 Primary Efficacy Analysis**

The primary analysis will be conducted in the ITT population. The primary efficacy endpoint is CDAI remission at Week 8 of the induction period. The null and alternative hypotheses for the primary endpoint are:

**H0**: There is no difference between the proportions of CDAI remission in MEDI2070 high dose group and placebo at Week 8 for subjects with moderate to severe CD who have failed or are intolerant to anti-TNF $\alpha$  therapy.

versus

**H1**: There is difference between the proportion of CDAI remission in MEDI2070 high dose group and placebo at Week 8 for subjects with moderate to severe CD who have failed or are intolerant to anti-TNF $\alpha$  therapy.

The primary comparison of interest will be MEDI2070 high-dose group versus placebo. The comparisons between MEDI2070 high-medium dose group versus placebo, low-medium dose group versus placebo, and MEDI2070 low dose group versus placebo will also be conducted. Nominal p-values will be presented without multiplicity adjustment.

P-values for comparisons between any MEDI2070 dose group and placebo will be obtained from a logistic regression model adjusting for prior anti-TNF $\alpha$  use (1 versus  $>1$ ). In the

event the number of remissions is too small (i.e.  $< 5$ ), the exact logistic regression will be performed instead. The statistical significant treatment effect will be tested against 2-sided alpha level of 0.10. The odds ratio and associated 90% confidence interval from the aforementioned logistic regression model will be presented.

In addition, the difference in CDAI remission rates at Week 8 between MEDI2070 dose groups and placebo group and associated 90% confidence interval will be provided using the logistic regression with delta method approach (Ge et al, 2011). In the event the number of remission is too small (i.e.  $< 5$ ), the unconditional exact confidence interval for the difference in CDAI remission at Week 8 between MEDI2070 dose groups and placebo group will be provided using Agresti and Ming (2001)'s approach via STATXACT. The pseudo SAS code can be found in the SPP.

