### **3.6.1.3 Additional Analyses of the Primary Efficacy Endpoint**

The following sensitivity analyses will be performed for the primary efficacy endpoints in the ITT population using the non-responder imputation:

1. A sensitivity analysis for the primary efficacy endpoint will be performed by extending the logistic regression model planned above via adjusting for baseline CDAI score. The odds ratio between each MEDI2070 dose group and placebo and associated 90% confidence interval will be presented.
2. A stratified Cochran-Mantel-Haenszel (CMH) row mean score test adjusting for prior anti-TNF $\alpha$  use (1 versus  $> 1$ ) will be conducted for the primary efficacy endpoint using the ITT population. In the event of small number of remissions (i.e.  $< 5$ ), the stratified conditional exact test will be performed via STATXACT. P-value, point estimate of common odds ratio and associated 90% mid-p corrected exact confidence interval will be presented.
3. Other baseline covariates will be explored by extending the logistic regression model via adjusting for baseline CDAI score and/or other baseline covariates. The following baseline covariates may be assessed and the final model will only include the significant baseline covariates ( $p < 0.10$ ). The odds ratio between each MEDI2070 dose group and placebo and associated 90% confidence interval from the logistic regression model will be presented.
  - Region (US, Non-US)
  - Disease duration

- Baseline CDAI score
- Baseline IL22
- [REDACTED]
- Baseline CRP
- Baseline weekly abdominal pain score
- Baseline weekly loose/liquid stool count
- Baseline SES-CD score
- Baseline fecal calprotectin
- Smoking status at baseline

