**Table 3.8-1 Summary of Efficacy Endpoints and Analyses**

Endpoints	Primary Analysis	Secondary/Sensitivity Analyses
Primary Efficacy Endpoint		
CDAI Clinical Remission at Week 8	
 
1. Summary statistics using non-responder imputation
 
2. Logistic regression (or exact logistic regression) with treatment and prior anti-TNF<math>\alpha</math> use as covariates using non-responder imputation
 
	
 
1. Logistic regression model adjusting for baseline CDAI score
 
2. CMH test or exact stratified test
 
3. Logistic regression model adjusting other baseline covariates
 
4. Predictive biomarker analysis
 
5. Cochran-Armitage trend test
 
6. MCP-Mod analysis
 

Secondary Efficacy Endpoints for DB induction period		
SES-CD remission at Week 16 PRO2 remission at Week 8 PRO2 remission at Week 16	
 
1. Summary statistics using non-responder imputation
 
2. Logistic regression (or exact logistic regression) with treatment and prior anti-TNF<math>\alpha</math> use as covariates using non-responder imputation
 
	
 
1. Logistic regression model adjusting for baseline SES-CD or PRO2 score
 
2. CMH test or exact stratified test
 
3. Logistic regression model adjusting other baseline covariates.
 
4. Predictive biomarker analysis
 
5. Cochran-Armitage trend test
 
6. MCP-Mod analysis
 

Endpoints	Primary Analysis	Secondary/Sensitivity Analyses

SES-CD response at Week 16 PRO2 response at Week 8 PRO2 response at Week 16 CDAI clinical remission at Week 16
	
1. Summary statistics using non-responder imputation  2. Logistic regression (or exact logistic regression) with treatment and prior anti-TNF<math>\alpha</math> use as covariates using non-responder imputation
	
1. Logistic regression model adjusting for baseline CDAI, SES-CD or PRO2 score 2. CMH test or exact stratified test 3. Logistic regression model adjusting other baseline covariates 4. Predictive biomarker analysis 5. Cochran-Armitage trend test

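### Planned 342-subject analysis: baseline CDAI could move from a sensitivity analysis, reported only as an odds ratio, into the primary Week 8 model at little cost, for a gain that is unproven and may be close to zero

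*Combined protocol and SAP*

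**What the plan says.** The file holds two SAPs. The earlier one plans the inferential analysis of about 342 subjects. The later one was written after the study stopped with 29 randomized and is descriptive. This point concerns the protocol and the earlier SAP; section numbers below refer to that SAP unless the later one is named.

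- **Primary model.** Protocol 4.8.4.1 says p-values "will be obtained from a logistic regression model adjusting for the number of prior" anti-TNF agents (1 vs >1). SAP 3.6.1.2 agrees: "obtained from a logistic regression model adjusting for prior anti-TNF" use. Table 3.8-1 lists treatment and prior anti-TNF use as the only terms.
- **Risk difference.** SAP 3.6.1.2 says that the difference in remission rates, with its 90% interval, "will be provided using the logistic regression with delta method approach". Appendix 6.3 describes the method: predict every subject's response under treatment and under control, average, and take the difference.
- **Baseline CDAI.** SAP 3.6.1.3, item 1, plans a sensitivity analysis "extending the logistic regression model planned above via adjusting for baseline CDAI score". Its output: "The odds ratio between each MEDI2070 dose group and placebo and associated 90% confidence interval will be presented". Table 3.8-1 repeats it as "Logistic regression model adjusting for baseline CDAI score". Item 3, the model with selected covariates, also names only an odds ratio.
- **Availability.** Protocol 4.3.1.1: "The CDAI will be calculated at the site in order to determine the eligibility for the study".
- **Missing baseline.** SAP 3.3.2 does not impute it.
- **Error control.** Protocol 4.8.1 and SAP 3.1 make all p-values nominal, tested at two-sided 0.10.

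**The concern.** The endpoint is the CDAI falling below 150, so a subject who enters with a high score has further to fall than one who enters near the lower limit. A prognostic link is plausible, though the documents do not quantify it. Randomization is stratified only on the number of prior anti-TNF agents, so chance imbalance in baseline CDAI is not controlled by design.

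If baseline CDAI is prognostic, the primary estimate gives up some precision and carries that imbalance. The adjusted analysis will be run, but its reported output is a conditional odds ratio. The 19-point difference in protocol 4.8.2 is on the risk-difference scale, where no baseline-adjusted estimate is named. That gap can be read directly from the text, whatever the prognostic strength.

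**Working it through.** **Inputs from the documents.** 76 per arm, 12% vs 31% remission, 10% dropout, two-sided alpha 0.10, stated power at least 85% (protocol 4.8.2). The moderate-to-severe CDAI band is taken from the cut-points in protocol 4.3.1.1 ("220 to 450 represent remission, mild disease, and moderate to severe disease, respectively").

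**Assumed.** The prognostic strength of baseline CDAI; a 50:50 stratum with log-odds -0.3; and the shape of the baseline distribution, since the entry cut-off is redacted.

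**Step 1: reproduce the stated power.** Power = Φ[(d - c - 1.645·SE0)/SE1], with SE0 pooled and SE1 unpooled.
- Dropouts as non-responders: 0.9 × 12% = 10.8% and 0.9 × 31% = 27.9%, so d = 0.171. SE0 = 0.0641, SE1 = 0.0626, c = 0. Power = 85.3%.
- 12% vs 31% with continuity correction c = 1/76: SE0 = 0.0666, SE1 = 0.0648. Power = 85.0%. Without the correction it is 89.2%.

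All three meet the claim of at least 85%. The documents do not show which route was used. The simulations below take 10.8% vs 27.9%.

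**Step 2: power with and without baseline CDAI, normal baseline.** 40,000 simulated trials per setting, Wald tests.

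| OR per SD | Gain, points | Gain with type I error matched at 10% |
|---|---|---|
| 1.0 | 0.0 | -0.1 |
| 1.25 | +0.2 | +0.1 |
| 1.5 | +0.8 | +0.6 |
| 2.0 | +1.9 | +1.4 |
| 3.0 | +4.5 | +4.1 |

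Type I error at nominal 10% is 9.1-9.3% for the stratum-only model and 9.4-9.7% for the adjusted one.

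**Step 3: baseline uniform over 220-450.** SD = 230/√12 = 66.4. For an OR per 100 points of θ, the OR per SD is θ^0.664 and the OR across the band is θ^2.3. 20,000 trials per setting.

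| OR per 100 points | OR per SD | OR across band | Gain, points | Matched gain | Risk-difference variance, stratum-only / adjusted | Models disagree at 0.10 |
|---|---|---|---|---|---|---|
| 1 | 1.0 | 1 | -0.2 | -0.5 | 0.99 | 1.3% |
| 1.5 | 1.31 | 2.5 | +0.2 | +0.2 | 1.00 | 2.0% |
| 2 | 1.58 | 4.9 | +0.5 | +0.3 | 1.02 | 3.1% |
| 3 | 2.07 | 12.5 | +2.1 | +2.0 | 1.07 | 4.8% |
| 5 | 2.91 | 40.5 | +3.7 | +3.6 | 1.13 | 6.6% |

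The Monte Carlo SE is about 0.1-0.2 points for the gain and 0.3 for the matched gain. In subjects per arm, 76 × (ratio - 1) is about 5 at a ratio of 1.07 and about 10 at 1.13.

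**Step 4: chance imbalance.** The SD of the between-arm mean difference is 66.4 × √(2/76) = 10.8 CDAI points, so P(|difference| > 13.3) = 22%. An imbalance of 13.3 points moves the unadjusted risk difference by 0.8, 1.3, 2.0 and 2.7 points at ORs of 1.5, 2, 3 and 5 per 100 CDAI points.

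**Step 5: side effects of the change.**
- *Odds ratio.* The median is 3.3 from the stratum-only model and 3.4, 3.5, 3.6 and 4.0 conditional on baseline at those same ORs. The estimand changes even when the risk difference does not.
- *Missing baseline (share assumed), OR 2 per 100 points.* Dropping those subjects changes power against the stratum-only model by +0.5, +0.2, -0.8 and -2.6 points at 1, 2, 5 and 10% missing. Mean imputation keeps +0.7 to +0.8 throughout.
- *Exact fallback at fewer than 5 remissions.* The text does not say whether the count is per arm or overall. If per arm, P(4 or fewer) is 8% for placebo (n = 76, 10.8%), and 61%, 51% and 10% for the low-dose arm (n = 38) at 10.8%, 12% and 20%. One table could then mix adjusted and unadjusted comparisons.

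**The case against.** The strongest reply is that this is a preference. The primary model adjusts for the only randomization stratum, the adjusted model is already pre-specified without selection, and p-values are nominal, so the choice of primary label changes a significance call in only about 1-7% of simulated trials. That is all correct. The gain is also unproven: at an OR per SD of 1.5 or less it is at or near simulation noise, and gains of 1.5 points or more need roughly a 12- to 40-fold difference in odds across the severity band, which nothing in the documents supports or excludes.

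The reply is also right that the change reaches further than the primary section. Dichotomous secondary endpoints are analyzed like the primary one, so the plan must say which model they use. The exact fallback could mix covariate sets, and a missing-baseline rule is needed. These are reasons to write the fix completely. They do not defeat it, because the loss is within noise when baseline CDAI is not prognostic and Appendix 6.3 extends directly to the larger model.

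A reader might infer that baseline CDAI adjustment is absent from the plan. It is not; it sits in sensitivity analysis 1.

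**Conclusion.** The point holds as a cheap, optional improvement to the planned 342-subject analysis. Assumed prognostic strength decides its size: about 0 to 1 power point at an OR per SD of 1.5 or less, about 1.5 to 4.5 points at 2 to 3, and essentially no loss at 1.0. The missing baseline-adjusted risk difference does not depend on that assumption.

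Three stronger readings are not supported:
- *The primary analysis is invalid or underpowered.* It adjusts for the stratum, its simulated type I error is below 10%, and the stated 85% reproduces.
- *A definite power gain is being lost.* The documents give no prognostic strength, and the gain may be nil.
- *The reported results of the stopped study are affected.* The later SAP summarizes the primary endpoint descriptively (3.6.1.2) and drops all sensitivity analyses (3.6.1.3).

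**What to change.** For the planned inferential analysis only, before unblinding:

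1. Make treatment, randomization stratum and continuous baseline CDAI the primary model for Week 8 CDAI remission. Lead with the standardized delta-method risk difference and its 90% interval (SAP 3.6.1.2, Appendix 6.3), and label the odds ratio as conditional on baseline CDAI.
2. Keep the stratum-only model as the sensitivity analysis and report it for all dose groups, so that any comparison that falls to the stratum-only exact method has a like-for-like row.
3. Fill missing baseline CDAI, expected to be rare, by treatment-blind mean imputation so that no ITT subject is dropped. Note this as an exception to SAP 3.3.2.
4. State that dichotomous secondary endpoints keep the stratum-only primary model, with their already planned baseline-adjusted sensitivity analyses.
5. Make matching edits in the protocol synopsis (statistical analyses), protocol 4.8.4.1 to 4.8.4.3, SAP 3.6.1.2, 3.6.1.3 and 3.6.2.2, and the primary and secondary rows of Table 3.8-1.

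If the primary model stays as it is, the minimum is to add the standardized risk difference and 90% interval to sensitivity analysis 1.

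Cost: several wording edits, one missing-covariate rule and an odds ratio with a conditional meaning. No new data or subjects are needed, and the sample-size statement and the later SAP stay as they are.

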##### **4.8.4.2 Additional Analyses of the Primary Endpoint**

A sensitivity analysis for the primary efficacy endpoint will be performed by extending the logistic regression model planned above via adjusting for baseline CDAI score and/or other baseline covariates for subjects in the ITT population. The following baseline covariates may be assessed and the final model will only include the significant baseline covariates.

- Age

- Sex
- Race
- Region (USA, non-USA)
- Baseline body mass index
- Disease duration
- Baseline CDAI score

- Baseline CRP
- Baseline fecal calprotectin
- Smoking status at baseline

A stratified Cochran Mantel Haenszel test adjusting for the number of prior anti-TNF $\alpha$  agents that failed or were not tolerated (1 vs > 1), or stratified exact test in the event of a small number of remissions, may also be performed. Missing data will be handled using the non-responder imputation method through the end of the double-blind induction and maintenance periods.

The dose-response trend for the double-blind induction period will be tested using a Cochran-Armitage trend test. Other dose-response models may be explored; ie, multiple comparison procedure modelling method. The details of the dose-response analysis will be described in the SAP.

[figure not shown]
The exposure-response trend for the placebo-controlled, double-blind, induction period will be tested. The details of the exposure-response analysis will be described in a separate document.

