## **4.6 Treatment Assignment and Blinding**

### **4.6.1 Methods for Assigning Treatment Groups**

For the double-blind induction and maintenance periods of the study, an IVRS/IWRS will be used to randomize subjects to a treatment arm, assign a unique randomization code, and assign investigational product kit numbers. A total of approximately 342 subjects will be randomized into 1 of 5 treatment groups:

- Treatment Group 1: MEDI2070 – high (76 subjects)
- Treatment Group 2: MEDI2070 – high-medium (76 subjects)
- Treatment Group 3: MEDI2070 – low-medium (76 subjects)
- Treatment Group 4: MEDI2070 – low (38 subjects)
- Treatment Group 5: Placebo (76 subjects)

Subjects will be stratified based on the number of prior anti-TNF $\alpha$  agents that failed or were not tolerated (1 vs > 1). The randomization will be based on permutation block algorithm. The maximum number of subjects within each stratum will not be set a priori.

During the 24-week, open-label period of the study, all subjects will receive 210 mg SC MEDI2070.

A subject is considered randomized into the study when the investigator notifies the IVRS/IWRS that the subject meets eligibility criteria and the IVRS/IWRS provides the assignment of blinded investigational product kit numbers to the subject.

Investigational product (MEDI2070 or placebo) must be administered the same day the investigational product is assigned. If there is a delay in the administration of investigational product such that it will not be administered within the specified timeframe, the study monitor must be notified immediately.

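### The dose-response trend test is named without the randomisation stratum; stratifying it is a free improvement that gains a little power if the stratum predicts remission

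*Combined protocol and SAP*

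**What the plan says.** Protocol section 4.6.1 describes the randomisation: "Subjects will be stratified based on the number of prior anti-TNF" agents failed or not tolerated (1 vs > 1). It adds: "The randomization will be based on permutation block algorithm" and "The maximum number of subjects within each stratum will not be set a priori".

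The pairwise analyses carry that factor. The logistic model for CDAI remission at Week 8 adjusts for it (protocol 4.8.4.1, original SAP 3.6.1.2). The CMH sensitivity test is expressly stratified by it (protocol 4.8.4.2, original SAP 3.6.1.3).

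For dose-response, which is a secondary objective (protocol 2.1.2.1, item 12), section 4.8.4.2 says: "The dose-response trend for the double-blind induction period will be tested using a Cochran-Armitage trend test". It mentions neither the stratum nor the dose scores, and continues: "The details of the dose-response analysis will be described in the SAP". Original SAP Table 3.8-1 lists "Cochran-Armitage trend test" as a secondary or sensitivity analysis for Week 8 CDAI remission and for several SES-CD, PRO2 and CDAI secondary endpoints. In the same column it lists a CMH or exact stratified test. The body of original SAP section 3.6.4.1 is blacked out apart from the MCP-Mod candidate models.

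**The concern.** Stratified blocks make the arms nearly identical in stratum mix. If the stratum is prognostic, the trend statistic then varies less from trial to trial than its pooled variance assumes. A test that ignores the stratum divides by too large a standard error and rejects a little too rarely.

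Two things would be at stake. One is some power for the dose-response objective. The other is consistency: as the visible text stands, the trend and the pairwise comparisons would rest on different adjustment bases.

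**Working it through.** **Inputs from the documents.** Arms 76/38/76/76/76 (placebo, low, low-medium, high-medium, high); Week 8 remission 12% on placebo and 31% on high dose (protocol 4.8.2); two-sided alpha 0.10: "The statistically significant treatment effect will be tested against two-sided alpha level of 0.10".

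**Assumptions.** The intermediate rates (15, 20, 25%), equal strata, scores 0-4 and every stratum odds ratio (OR) are assumptions. The documents give no remission rate by stratum.

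**Step 1: the plan's own figure.** The documents state no power for the trend test, only at least 85% for high dose versus placebo. The pooled mean rate is 0.215. Without continuity correction,

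n' = [1.645·√(2·0.215·0.785) + 1.036·√(0.12·0.88 + 0.31·0.69)]² / 0.19² = 65.8.

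With correction,

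n = (n'/4)·[1 + √(1 + 4/(n'·0.19))]² = 76.0.

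The stated 76 per arm reproduces, so the planning rates are a sound basis.

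**Step 2: size by formula.** Let R² be the share of outcome variance explained by the stratum. The plain test's size is about 2·[1 − Φ(1.645/√(1 − R²))].

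- OR 2.7, 12% remission overall: stratum rates 17.0% and 7.0%; R² = 0.25·(0.170 − 0.070)²/(0.12·0.88) ≈ 0.023; size 0.096.
- OR 2.7, 20% overall: stratum rates 27.6% and 12.4%; R² ≈ 0.036; size 0.094.

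**Step 3: simulation.** 600,000 trials per setting, each arm split equally between strata, arm rates held fixed while the OR varies. The plain statistic is Cochran-Armitage. The stratified one sums score minus expectation over strata and divides by the root of the summed within-stratum (hypergeometric) variances. Simulation error is √(0.94·0.06/600,000) ≈ 0.03 points near 94% and √(0.25/600,000) ≈ 0.06 points near 50%. Half effect means 12/13.5/16/18.5/21.5%.

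| Stratum OR | Power %, full effect: plain / stratified (gain) | Power %, half effect: plain / stratified (gain) |
|---|---|---|
| 1 | 93.99 / 93.93 (−0.06) | 53.23 / 53.07 (−0.16) |
| 1.5 | 93.97 / 93.97 (0.00) | 53.37 / 53.40 (0.03) |
| 2.7 | 94.28 / 94.57 (0.29) | 53.29 / 54.22 (0.93) |
| 5 | 94.74 / 95.45 (0.71) | 53.37 / 55.61 (2.24) |
| 7.4 | 95.11 / 96.08 (0.97) | 53.37 / 56.62 (3.25) |

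| Stratum OR | Size at 12%: plain / stratified | Size at 20%: plain / stratified |
|---|---|---|
| 1 | 0.102 / 0.101 | 0.100 / 0.099 |
| 1.5 | 0.101 / 0.101 | 0.098 / 0.100 |
| 2.7 | 0.097 / 0.100 | 0.093 / 0.101 |
| 5 | 0.093 / 0.099 | 0.086 / 0.100 |
| 7.4 | 0.090 / 0.098 | 0.080 / 0.100 |

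A separate run of 200,000 trials gave 0.098 at 12% and 0.094 at 20% for OR 2.7. The range for that setting is therefore about 0.093 to 0.098.

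**Step 4: sensitivity.**
- Unequal strata (30/70), linear trend from 12% to 31%: 94.2% vs 94.5% at OR 3, and 94.7% vs 95.5% at OR 5.
- First-dose mg scores (0/70/210/280/700), equal strata, OR 3: gain of 0.4 points for a trend linear in mg (93.4% to 93.7%) and 0.7 for one linear in rank (88.9% to 89.5%), before rounding.
- The hypergeometric variance in the plain test as well: half-effect gains of 1.2, 2.5 and 3.5 points at OR 2.7, 5 and 7.4.
- Simple instead of stratified randomisation, OR 5, 12% remission: plain size 0.102. The conservatism comes from stratifying the randomisation and not the test.

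**The case against.** The strongest reply has four parts.

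1. Unstratified is an inference. The protocol defers the detail to the SAP, the SAP section that should hold it is blacked out, and a table label is not a specification. This stands as a limit: the stratum may already be there. Against it, the protocol and the table both say stratified for the CMH test and do not say it for the trend test.
2. The effect is trivial unless the stratum is strongly prognostic, and nothing in the documents shows that it is. This stands. At an odds ratio of 1 the plain test is better by about 0.1 to 0.2 points.
3. The trend test is supportive, p-values are nominal (protocol 4.8.1), MCP-Mod sits beside it for the main remission endpoints, and the primary comparison is already adjusted. This also stands. It makes the point an improvement and not an error.
4. The analysis was cancelled. The SAP written after early termination drops it (section 3.6.4.1). This stands too, so no result of this trial changes.

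A reader might go further and infer a loss of about five points of power. Such a figure appears if the two strata are placed at logit shifts of ±1.5 (OR 20) around the planned rates: about 87.6% vs 92.5%. The arms then no longer average 12 to 31% but 20.4/24.0/29.1/33.4/38.0%, which is not the planned scenario. With arm rates held at the planned values, the same odds ratio gives about 95.8% vs 97.2%, a gain of about 1.4 points, and the documents do not support an odds ratio of that size in any case.

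**Conclusion.** The point holds as a minor efficiency and consistency improvement to the plan as designed. If number of prior anti-TNF agents predicts remission, the plain test is slightly conservative. Stratifying gains at most about 0.3 points of power at the planned effect for stratum odds ratios up to 2.7, and about 1 point at 7.4. The gain matters more where power is not near its ceiling, reaching about 3.2 points at half the effect and an odds ratio of 7.4. All of this rests on assumed stratum odds ratios, stratum shares, intermediate rates and scores.

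A reader might infer that the trend test is invalid, or that the plan certainly leaves the stratum out. The documents support neither. Omitting the stratum lowers the rejection rate under the null and does not raise it, and the redacted SAP text may already stratify.

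**What to change.** In protocol section 4.8.4.2 and original SAP Table 3.8-1, name the stratified trend statistic (Mantel extension, 1-df CMH correlation), stratified by number of prior anti-TNF agents (1 vs > 1) and using the same dose scores as planned for the plain test. If original SAP section 3.6.4.1 already specifies this, only the protocol and table wording needs aligning.

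The cost is one line of text and one stratum variable in the program. The data are already collected at randomisation. If the stratum is not prognostic, the price is about 0.1 to 0.2 points of power. Nothing needs to change in the SAP written after early termination.
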